# 3.4.1. Subject Subgroups for Efficacy Analyses

The proportion of subjects with HIV-1 RNA < 50 copies/mL at Week 48 will be analyzed for the following subject subgroups (also see Section 6.1.2.2.2 for details):

- Age (years): (a)  $\leq 50$  and (b)  $\geq 50$
- Sex: (a) male and (b) female
- Race: (a) black and (b) nonblack
- Region: (a) US and (b) Ex-US
- Study drug adherence (%): (a)  $\leq$  95 and (b)  $\geq$  95 (based on adherence up to Week 48 Visit)
- Baseline NRTI resistance (determined based on virology data): (a) No NRTI mutation (b) any NRTI mutation
- Baseline NRTI resistance (determined based on virology data): (a) No NRTI mutation,
   (b) K65R/E/N or ≥ 3 TAMs (c) any other pattern of NRTI mutation
- Baseline M184I/V resistance (determined based on virology data): (a) No M184I/V mutation (b) any M184I/V mutation

The proportion of subjects with HBV Deoxyribonucleic Acid (DNA) < 29 IU/mL at baseline and Week 48 and the change from baseline in  $log_{10}$  HBV DNA by visit will be analyzed for the following subject subgroup:

• Subjects with HIV/HBV coinfection at baseline

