The CMH analysis will be used to estimate the odds ratio and corresponding 95% CI for each region and overall. The homogeneity of the odds ratios across different regions will be tested using a Breslow-Day test and a corresponding p value will be reported.

6.1.2.2.2. Subgroup Analysis of the Proportion of Subjects with HIV-1 RNA < 50 copies/mL at Week 48 as Determined by US FDA-defined Snapshot Algorithm

Since the proportion of subjects with HIV-1 RNA  $\geq$  50 copies/mL at Week 48 as determined by the US FDA-defined snapshot algorithm (primary endpoint) is expected to be very low (around 2%), the efficacy analysis by subgroup will be conducted by assessing the proportion of subjects with HIV-1 RNA < 50 copies/mL determined by the US FDA-defined snapshot algorithm at Week 48 (a secondary efficacy endpoint) within each subgroup specified in Section 3.4.1 based on the FAS for randomized phase analysis.

For each level of subgroup factors, the proportion difference between treatment groups and the associated 2-sided 95% CIs will be computed based on an unconditional exact method using 2 inverted 1-sided tests.

Additionally, a logistic regression model will be performed which include subgroup, treatment, and treatment by subgroup interaction. The odds ratio and the associated 95% CI will be estimated within each subgroup. The homogeneity of the treatment effects between subgroups will be evaluated using a Wald test based on the interaction between treatment and the subgroup factor.

A forest plot of the treatment differences in HIV-1 RNA < 50 copies/mL (US FDA-defined snapshot algorithm) at Week 48 and their associated 95% CIs for each subgroup will be generated.

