   tables trtgrp*response/fisher; /*p value from Fisher's exact test*/
run;
```

f) Homogeneity test: Homogeneity Test of Treatment Effect (HIV-1 RNA < 50 copies/mL by US FDA-defined snapshot algorithm) Across Region in HIV-1 RNA < 50 copies/mL at Week 48 (Snapshot Algorithm). For each region, the odds ratio and its 95% CI are calculated from the CMH test. For overall, the odds ratio and its 95% CI are calculated based on the common odds ratio estimate from the CMH test. The p-value for the homogeneity test is based on the Breslow-Day test of the interaction between region and treatment group as follows.

```
proc freq data=xxx;
  tables region*trtgrp* response /all; /*p value from Breslow Day test,
  (trtgrp: 1, 2; response: 1: < 50, 2: >=50)*/
run;
```

g) Subgroup analyses for HIV-1 RNA < 50 copies/mL by US FDA-defined snapshot algorithm

For the subgroups of age, sex, race, baseline CD4 cell count, and study drug adherence, the proportion difference between two treatment groups and its 95% CIs are calculated based on an unconditional exact method using 2 inverted 1-sided tests, similarly to that for the primary efficacy endpoint.

- h) Homogeneity test: Homogeneity Test of Treatment Effect (HIV-1 RNA < 50 copies/mL by US FDA-defined snapshot algorithm) between Subgroups in HIV-1 RNA < 50 copies/mL at Week 48 (Snapshot Algorithm)
  - a. For the subgroups of age, sex, race, region and study drug adherence, the odds ratio and the associated 95% CIs are estimated for the response variable (response; coded as 1 for success and 0 for non-success) using a logistic regression model including subgroup factor (coded as 1 for the first subgroup and 2 for the second subgroup), treatment (trtgrp; coded as 1 for active [ie, B/F/TAF] and 2 for control), and treatment by subgroup factor.

```
eg. region stratum (region; coded as 1 for "US" and 2 for "Ex-US")
```

For example, for the age subgroup (agegrp; coded as 1 for < 50 and 2 for >= 50), the following SAS code will be used to generate the Odds Ratio and its 95% CI within the subgroup:

Note: For the following code, it is assumed that none of the variables have any formats applied to them. If they do, they must be removed before calling the code.

e.g. for the age subgroup, the following codes will be used to get Odds Ratio and 95% CI within subgroup:

```
proc genmod data=data descending; /*model for success*/
class trtgrpn agegrp;
model response = trtgrpn agegrp trtgrpn*agegrp/dist=bin
link=logit lrci;

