estimate 'Group 1' trtgrpn 1 -1 trtgrpn*agegrp 1 0 -1 0/exp;
estimate 'Group 2' trtgrpn 1 -1 trtgrpn*agegrp 0 1 0 -1/exp;
run;
```

Note: trtgrpn is the numeric treatment group variable, response is the response outcome variable (1 vs 0 ('<50' vs'>=50')), agegrp is the subgroup variable for age (1:<50 vs 2: >=50).

(P-value for the homogeneity test was based on the Wald test of the interaction between treatment and subgroup. Odds ratio is from L'Beta estimate, its 95%CI is from L'Beta confidence limits for each subgroup.)

i) ANOVA model for continuous efficacy variable (eg, CD4): The differences in changes from baseline in CD4 cell count between treatment groups and the associated 95% CI will be constructed using an ANOVA, including treatment as fixed effect in the model.

```
proc glm data=adeff;
     class trtgrp;
     model CD4=trtgrp;
     lsmeans trtgrp /alpha=0.05 cl pdiff;
run;
```

j) Listing for US FDA-defined snapshot outcome:

In addition to flagging the values of HIV-1 RNA < 50 or  $\ge 50$  copies/mL for virologic outcomes, flag the last available HIV-1 RNA value while on treatment for the following categories:

- i) HIV-1 RNA >= 50 copies/mL Discontinued Study Drug Due to AE or Death and Last Available HIV-1 RNA >= 50 copies/mL
- ii) HIV-1 RNA >= 50 copies/mL Discontinued Study Drug Due to Other reason\* and Last Available HIV-1 RNA >= 50 copies/mL
- iii) No virologic Data Discontinued Study Drug Due to AE or Death and Last Available HIV-1 RNA < 50 copies/mL
- iv) No virologic Data Discontinued Study Drug Due to Other reason\* and Last Available HIV-1 RNA < 50 copies/mL
- Note: \* Other reasons include subjects who discontinued study drug due to investigator's discretion, subject decision, lost to follow-up, noncompliance with study drug, protocol violation, pregnancy, and study terminated by sponsor.
- 15) Clarification of the following LOCF algorithms:
  - Baseline values will be carried forward.
  - For CD4:

If a value is missing in an analysis visit window, replace the missing value with the last on-treatment value observed before the analysis visit window that has the missing value.

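### The Wald homogeneity test for HIV-1 RNA < 50 gives p near 1 when one arm of a two-level subgroup has no non-responders, and Appendix 8 lists different subgroups from SAP 3.4.1

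*SAP*

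**What the plan says.** SAP 6.1.2.2.2 fits a logistic model with treatment, subgroup and their interaction for every factor in Section 3.4.1. Homogeneity of the treatment effect "will be evaluated using a Wald test based on the interaction between treatment and the subgroup factor". Appendix 8 item 14(h) confirms it: "P-value for the homogeneity test was based on the Wald test of the interaction between treatment and subgroup". On the odds ratio it says "Odds ratio is from L'Beta estimate, its 95%CI is from L'Beta confidence limits for each subgroup", which are also Wald limits. The printed model statement includes "link=logit lrci", so profile-likelihood limits for the model parameters are requested, but the reporting note does not use them. Nothing is said about an arm with no non-responders.

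A second homogeneity test appears in SAP 6.1.2.2.1: "The homogeneity of the odds ratios across different regions will be tested using a Breslow-Day test". The regions there are the eight in Appendix 3, so the test does not cover the resistance factors.

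Section 3.4.1 lists age, sex, race, region (US/Ex-US), adherence, NRTI resistance in two levels, NRTI resistance in three levels ("b) K65R/E/N or ≥ 3 TAMs (c) any other pattern of NRTI mutation" after no mutation), and "Baseline M184I/V resistance (determined based on virology data): (a) No M184I/V mutation (b) any M184I/V mutation". Item 14(h) has a shorter list: "For the subgroups of age, sex, race, region and study drug adherence, the odds ratio and the associated 95% CIs are estimated". Item 14(g) lists age, sex, race, baseline CD4 and adherence.

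**The concern.** A one-degree-of-freedom Wald test divides the estimated interaction by its standard error. With an empty cell the maximum-likelihood estimate does not exist, and the reported p-value shows only where the fitting algorithm stopped. A homogeneity p of 0.999 would be read as no sign that the effect differs, when the model could not estimate the difference.

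This is most likely in a small level. The primary objective covers subjects with or without antiretroviral resistance, so the resistance and M184I/V factors are the ones a reader would look at, and their levels may be small.

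The differing subgroup lists are a separate, editorial matter. A programmer working only from Appendix 8 would not produce the resistance and M184I/V results that 6.1.2.2.2 requires.

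**Working it through.** **Inputs.** The SAP gives no figure for this test, so there is none to reproduce. From Appendix 3, US = 83 + 64 + 33 + 82 + 67 + 102 = 431 and Ex-US = 49 + 85 = 134, about 67 Ex-US per arm if split evenly. All response counts, and the sizes of the resistance and M184I/V levels, are assumptions. The documents do not give them.

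**Formula.** For a two-level factor the model is saturated. With s responders and f non-responders in each of the four cells, the interaction is the difference between levels in [log(s/f) for B/F/TAF minus log(s/f) for DTG+F/TAF]. Its variance is the sum of 1/s + 1/f over the four cells. As one f goes to 0, the estimate grows like log(1/f) and the SE like 1/√f. The ratio goes to 0 and p goes to 1.

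**A table without an empty arm.** US 205/216 v 204/215, Ex-US 58/67 v 66/67 (B/F/TAF first):
- Ex-US: log(58/9) − log(66/1) = 1.863 − 4.190 = −2.327
- US: log(205/11) − log(204/11) = 0.005
- Interaction = −2.327 − 0.005 = −2.33
- SE = √(1/58 + 1/9 + 1/66 + 1/1 + 1/205 + 1/11 + 1/204 + 1/11) = √1.335 = 1.16
- Wald p = 0.044; Firth 0.025

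**The same table with 67/67.** The evidence of a difference is now stronger. The software returns an interaction of −22.7 with SE 16,005, so Wald p = 0.999. The likelihood-ratio p is 0.0013 and the Firth likelihood-ratio p is 0.0049. For this saturated model the Firth test equals the likelihood-ratio test after adding 0.5 to every cell. The 95% profile-likelihood upper limit for the interaction, which the printed code would produce, is −1.40 and excludes 0. The Firth odds ratio for Ex-US is 0.046 (0.0004 to 0.37), whereas the Wald interval is uninformative.

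**Other tables.**

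| Table (B/F/TAF v DTG+F/TAF) | Wald | LR | Firth |
|---|---|---|---|
| M184I/V 20/25 v 25/25; 244/257 in each arm elsewhere | 0.999 | 0.010 | 0.032 |
| Three-level NRTI (214/14/54 per arm), only 9/14 v 14/14 differs | 1.000 | – | 0.076 |
| Same, with 40/54 v 53/54 in the third level | 0.038 | 0.0007 | 0.003 |

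For the three-level factor the joint Wald test can still reject, but the level with the empty arm contributes nothing.

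**Breslow-Day is no substitute.** The same 9 v 0 Ex-US failures, spread four ways over Regions 1 and 2 of the eight in Appendix 3, give p from 0.30 to 0.38.

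**How often an arm is empty.** P(a given arm of size n is empty) = (1 − q)^n for non-response rate q. At q = 2 / 5 / 10% this is 75 / 49 / 23% for n = 14 and 26 / 3 / 0.1% for n = 67.

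**Rejection rates.** 20,000 simulated trials per scenario, 282 per arm in total, 95% response in the other level. Entries are the percentage with p < 0.05, Wald / Firth:

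| Per arm in the level | No interaction | 85% v 95% | 75% v 95% |
|---|---|---|---|
| 14 | 0.02 / 0.6 | 0.4 / 6.5 | 3.2 / 22.1 |
| 25 | 0.1 / 1.6 | 3.6 / 14.5 | 17.3 / 41.5 |
| 40 | 0.6 / 3.0 | 11.6 / 23.0 | 42.1 / 57.5 |
| 67 | 2.0 / 4.3 | 27.8 / 33.1 | 67.4 / 71.8 |

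Whenever one arm was empty, Wald rejected in none of the runs. At 85% v 95%, an empty arm together with Firth p < 0.05 occurred in 5.9 / 9.7 / 8.6 / 3.2% of trials for 14 / 25 / 40 / 67 per arm.

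**The case against.** The sponsor did allow for sparsity. It moved subgroup analysis from HIV-1 RNA ≥ 50, expected at about 2%, to HIV-1 RNA < 50, where non-response also includes subjects with no virologic data. The 2% column above may therefore overstate the chance of an empty arm. At 67 per arm and 5% non-response or more, a given arm is empty at most 3% of the time.

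The planned displays would also expose the problem. In the Ex-US example the exact risk difference is −13.4% (−24.0 to −6.0), and for M184I/V it is −20.0% (−40.7 to −4.1). An odds ratio with an unbounded interval is visibly degenerate.

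The replacement test gains little in very small levels. At 14 per arm and 85% v 95%, Firth still misses the difference 93.5% of the time, and with an empty arm it needs at least 5 v 0 failures to reach 0.05. The choice of replacement can also decide significance: 4 v 0 Ex-US failures give 0.025 by likelihood ratio and 0.073 by Firth.

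These points stand, and they are why the matter is minor. None of them defends the Wald p, which rises to about 1 as the evidence strengthens from 66/67 to 67/67. That likelihood ratio and Firth can disagree is a reason to name one test, not to keep one that fails at the boundary.

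The list mismatch is editorial, because 6.1.2.2.2 refers to Section 3.4.1 and governs.

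**Conclusion.** The concern holds, as a minor point. That the Wald p goes to about 1 for a two-level factor with one empty arm follows from algebra and does not depend on the assumed counts. The assumptions affect only how often it happens and how much it hides. On the ranges shown, the loss is largest at 14 to 40 per arm and modest at 67 (27.8% v 33.1% at 85% v 95%). If both arms of a level are empty, the likelihood-ratio p is also 1, so nothing is hidden. For the three-level factor the joint test is not forced to 1, but it ignores the empty level.

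No decision rule or non-inferiority conclusion uses this p-value. The differences between Appendix 8 and Section 3.4.1 are plain on the page.

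**What to change.** In SAP 6.1.2.2.2 and Appendix 8 item 14(h), replace the Wald p with one named test: the Firth-penalised likelihood-ratio test of the interaction, joint over all levels for the three-level NRTI factor. Take the within-subgroup odds-ratio intervals from the penalised profile likelihood. Keep the exact risk-difference intervals and forest plot as the main display.

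Match the lists to Section 3.4.1:
- Add two- and three-level NRTI resistance and M184I/V to 14(g) and 14(h).
- Add region to 14(g).
- Remove baseline CD4 from 14(g), or list it in 3.4.1.

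The cost is a few lines of code and wording. Firth is conservative in very small levels: 0.6% rejection under no interaction at 14 per arm, and 0.076 in the three-level example. SAP 2.2.1 says the Week 48 analysis has already been conducted, so the results must be labelled as changed after it.

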## 6.1.2.2.3 Analysis of CD4+ Cell Count

All CD4+ cell count will be summarized by visit using observed, on-treatment data (ie, data collected up to 1 day after permanent discontinuation of blinded study drug) for subjects in the FAS for randomized phase analysis and for subjects in all B/F/TAF Analysis Set for all B/F/TAF analysis.

The changes from baseline in CD4+ cell count at Week 48 will be summarized by treatment group using descriptive statistics for randomized phase analysis. The differences in changes from baseline in CD4+ cell count between the 2 treatment groups and the associated 95% CI will be constructed using analysis of variance (ANOVA) models, including treatment group as a fixed effect in the model. The change from baseline in CD4+ cell count will also be summarized at visits other than Week 48 by treatment group for the FAS for randomized phase analysis.

The change from baseline in CD4+ cell counts will also be analyzed based on the Week 48 PP analysis set for randomized phase analysis.

[figure not shown]
The mean and 95% CI of change from baseline in CD4+ cell count over time will be plotted for the FAS for randomized phase analysis.

In addition, the change from baseline in CD4+ cell counts with missing values imputed using the last observation carried forward (LOCF) method will be summarized at each visit (up to week 48 visit) based on the FAS for randomized phase analysis. The algorithm for LOCF is as follows:

- If a value is missing in an analysis visit window, the missing value will be replaced with the
  last on-treatment value (ie, data collected up to 1 day after permanent discontinuation of
  study drug) observed before the analysis visit window that has the missing value.
- Baseline values will be carried forward to impute the postbaseline value at a specific visit, if there is no non-missing postbaseline observation collected prior to that visit.

The changes from baseline in CD4+ cell count will be summarized by treatment group and scheduled visits using descriptive for all B/F/TAF analysis.

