#### **Statistical Methods:**

The primary analysis will consist of a non-inferiority test of switching to B/F/TAF FDC versus DTG+F/TAF, with respect to the proportion of subjects with HIV-1 RNA ≥ 50 copies/mL at Week 48, as defined by the US FDA-defined snapshot algorithm. It will be concluded that B/F/TAF FDC is non-inferior to DTG+F/TAF if the upper bound of the 2-sided 95% confidence interval (CI) of the difference between treatment groups [B/F/TAF – (DTG+F/TAF)] in the percentage of subjects with HIV-1 RNA ≥ 50 copies/mL is less than 4% (ie, a margin of 4% is applied to non-inferiority assessment). The 2-sided 95% CIs will be constructed based on the exact method.

The proportion of subjects with HIV-1 RNA < 50 copies/mL at Week 48 as defined by the US FDA-defined snapshot algorithm will also be summarized. The 95% CIs will be constructed in the same manner as described for the primary efficacy endpoint.

The change from baseline in CD4+ cell count at Week 48 will be summarized by treatment using descriptive statistics. The differences and the associated 95% CIs will be constructed using an Analysis of Variance (ANOVA) model, including treatment (B/F/TAF vs. DTG+F/TAF), prior NRTI use (F/TAF vs. F/TDF), and documented or suspected history of NRTI resistance as fixed effects in the model.

Adverse events and clinical laboratory assessment will be summarized using descriptive statistics.

Patient reported outcome instrument assessments may be summarized using descriptive statistics.

A total of approximately 520 HIV-1 infected subjects, randomized in a 1:1 ratio to 2 treatment groups (260 subjects per treatment group), achieves at least 90% power to detect a non-inferiority margin of 4% in difference in percentage of subjects with HIV-1 RNA  $\geq$  50 copies/mL at Week 48 between the 2 treatment groups.

For sample size and power computation, it is assumed that both treatment groups have 2% of subjects with HIV-1 RNA  $\geq 50$  copies/mL at Week 48 (based on the historical Gilead Genvoya® and Stribild® studies), that a non-inferiority margin is 4%, and that the significance level of the test is at a one-sided 0.025 level.

This study will be conducted in accordance with the guidelines of Good Clinical Practice (GCP) including archiving of essential documents.

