#### 8.5.2. Secondary Analyses

The proportion of subjects with HIV-1 RNA < 50 copies/mL at Week 48 as defined by the US FDA-defined snapshot algorithm will also be summarized. The 95% CIs will be constructed in the same manner as described for the primary efficacy endpoint. However, non-inferiority will be assessed using a margin of 10%. It will be concluded that B/F/TAF FDC is noninferior to DTG+F/TAF if the lower bound of the 2-sided 95% CI of the difference between treatment groups (B/F/TAF group – DTG+F/TAF group) in the response rate is greater than -10%.

The change from baseline in CD4+ cell count at Week 48 will be summarized by treatment using descriptive statistics. The differences and the associated 95% CIs will be constructed using an Analysis of Variance (ANOVA) model, including treatment (B/F/TAF group vs. DTG+F/TAF group), prior NRTI use (F/TAF vs. F/TDF) and history of NRTI resistance as fixed effects in the model.

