# 1. INTRODUCTION

This statistical analysis plan (SAP) describes the statistical analysis methods and data presentations to be used in tables, figures, and listings (TFLs) of final analysis for Study GS-US-380-4030, which will be performed when all subjects have completed the study or prematurely discontinued from the study. This SAP is based on the study protocol amendment 2 dated 28 June 2018 and the electronic case report form (eCRF). The SAP will be finalized before database finalization. Any changes made after the finalization of the SAP will be documented in the clinical study report.

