#### 3.3. Strata and Covariates

Randomization was stratified by prior NRTI backbone use (F/TAF vs. F/TDF) and documented or suspected history of NRTI resistance. For analysis, the baseline NRTI resistance stratum was re-classified based on virology data collected at both screening and/or baseline:

Baseline NRTI resistance stratum are as follows:

1) No NRTI mutation:

None of these following mutations/no NRTI resistance

2) K65R/E/N or  $\geq$  3 TAMs:

K65R/E/N or  $\geq$  3 TAMs that include M41L, L210W, or T69 insertions: K65R/E/N, or 3 or more thymidine analogue mutations (TAMs) that include M41L or L210W, or T69 insertions, (TAMs are: M41L, D67N, K70R, L210W, T215F/Y, and K219Q/E/R/N)

3) Any other pattern of NRTI mutation:

Any other pattern of NRTI resistance of M41L, D67N, K70R, L74I/V, Y115F, Q151M, M184I/V, L210W, T215F/Y, K219Q/E/R/N, T69D, K70E/G/M/Q/S/T, V75A/S/M/T

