# 4. SUBJECT DISPOSITION

## 4.1. Subject Enrollment and Disposition

## 4.1.1. Subject Enrollment

The number and percentage of subjects randomized at each region, country, and investigator will be summarized by treatment group and overall using the safety analysis set. The region definition is provided in Appendix 2. The denominator for this calculation will be the number of subjects in the safety analysis set. Similarly, the number and percentage of subjects enrolled in each randomization stratum will be summarized based on reclassified strata using baseline NRTI backbone based on the Non-Study ARV Medication eCRF, and baseline NRTI resistance data as determined by Gilead Virology based on virology data instead of using interactive web response system (IWRS) data.

If there are discrepancies between IWRS and collected data with regard to stratum assignment, a listing of the discrepancies will be provided.

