## 6.3. Changes From Protocol-Specified Efficacy Analyses

No change from the protocol-specified efficacy analysis is planned.

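### The SAP fits the Week 48 CD4+ change with treatment only, the protocol also includes both randomisation strata, and SAP 6.3 reports no change.

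*SAP*

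**What the plan says.** Protocol 8.5.2 builds the CD4+ comparison from an ANOVA that contains treatment plus "prior NRTI use (F/TAF vs. F/TDF) and history of NRTI resistance as fixed effects in the model". The synopsis gives the same three terms and words the last one as "documented or suspected history of NRTI resistance as fixed effects in the model". Protocol 5.1 shows that prior NRTI use (two levels) and NRTI resistance (three categories) are the randomisation strata.

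SAP 6.1.2.2.3 says the difference and CI are "constructed using analysis of variance (ANOVA) models, including treatment group as a fixed effect in the model". Appendix 8 item 14i repeats this, "constructed using an ANOVA, including treatment as fixed effect in the model", and its PROC GLM call has one class variable and the line `model CD4=trtgrp`.

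The SAP identifies its source: "This SAP is based on the study protocol amendment 2 dated 28 June 2018". Section 6.3, which exists to declare departures, says: "No change from the protocol-specified efficacy analysis is planned". The revision table in SAP section 11 is empty.

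SAP 3.3 adds: "For analysis, the baseline NRTI resistance stratum was re-classified based on virology data collected at both screening and/or baseline".

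**The concern.** The change from baseline in CD4+ count at Week 48 is one of two named secondary efficacy endpoints. The protocol defines one model for it and the SAP defines another, while the section that should reconcile them denies any difference. A reader who compares the protocol with the study report will find a different model and a SAP statement that nothing changed. Nothing shows whether the factors were removed before or after the Week 48 results were known.

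This ANOVA was also the only efficacy model in the protocol that used the strata. Under the SAP, no overall between-arm efficacy estimate adjusts for either stratification factor.

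The possible statistical consequence is a slightly wider and slightly conservative CI, because the randomisation balances factors that the model then ignores.

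**Working it through.** **1. Model terms side by side**

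| Source | Treatment | Prior NRTI use | NRTI resistance |
|---|---|---|---|
| Protocol synopsis | yes | yes | yes |
| Protocol 8.5.2 | yes | yes | yes |
| SAP 6.1.2.2.3 | yes | no | no |
| SAP Appendix 8 item 14i, text | yes | no | no |
| SAP Appendix 8 item 14i, code | yes | no | no |

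The SAP's section text, its programming text and its code all agree, so this is not merely a shortened sentence.

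**2. Are the strata handled elsewhere in the efficacy analysis?** Not in an overall comparison. The two HIV-1 RNA endpoints use an unstratified exact method (SAP 6.1.1.4 and 6.1.2.2.1). The CMH analysis is stratified by region. NRTI resistance appears in efficacy subgroups for HIV-1 RNA below 50 copies/mL (SAP 3.4.1). Prior NRTI backbone appears only in safety subgroups (SAP 3.4.2).

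**3. Size of the effect.** The documents state no precision, margin or power for CD4+ change, so there is no figure of the plan's own to reproduce. Let R² be the share of variance in CD4+ change explained by the two factors. It is not given and is assumed here.

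- Width of the treatment-only CI relative to the protocol model: 1/√(1 − R²).
- Coverage of the treatment-only CI when the strata are balanced by design: 2Φ(1.96/√(1 − R²)) − 1.

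| R² (assumed) | Width ratio | Coverage |
|---|---|---|
| 0 | 1.000 | 95.0% |
| 0.01 | 1.005 | 95.1% |
| 0.02 | 1.010 | 95.2% |
| 0.05 | 1.026 | 95.6% |

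**4. Simulation check.** There were 6,000 trials per R² value with N = 565 (the FAS size in SAP Appendix 3). Assumptions: permuted blocks of 4 within six strata, shares of 70/30 and 4/20/76, and R² split equally between the factors. Mean width ratios were 1.000, 1.005, 1.010 and 1.026. Coverage was 95.5, 94.8, 95.1 and 95.5% for treatment only, and 95.5, 94.7, 95.0 and 95.0% adjusted (Monte Carlo SE 0.3 percentage points). Mean estimates were within 0.001 SD of the truth for both models, so there is no sign of bias.

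**5. Illustration in cells/µL.** The only SDs for CD4+ change in the documents come from the Phase 2 study in treatment-naive subjects (protocol 1.2.3.3): 221.7 and 242.0. Using n = 65 and 33:

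- Pooled SD = √[(64 × 221.7² + 32 × 242.0²)/96] = 228.7.
- Treatment-only half-width at 565/2 = 282.5 per arm = 1.96 × 228.7 × √(2/282.5) = 37.7.
- Adjusted half-width at R² = 0.05 = 37.7 × √0.95 = 36.8, a difference of about 1 cell/µL.
- Adjusted half-width at R² = 0.10 = 37.7 × √0.90 = 35.8, a difference of about 2 cells/µL.

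**The case against.** The strongest reply is that nothing in the trial turns on this. CD4+ change has no margin, hypothesis or decision rule, and SAP 3.5 assigns alpha only to the two HIV-1 RNA endpoints. The treatment-only estimate is unbiased and its CI errs on the safe side. This stands, and it limits the point to one of traceability with a minor loss of precision.

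A second reply concerns timing. This SAP covers the final analysis, and SAP 2.2.1 says the Week 48 analysis has already been done. Restoring the factors now could produce a second estimate beside one already reported. That is a fair caution. However, returning to a model fixed in the protocol is not a new choice made after unblinding, and the alternative of keeping treatment only and declaring it is open. The documents do not show which model the completed Week 48 analysis used.

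Third, the re-classified resistance stratum in SAP 3.3 is not idle: it feeds two efficacy subgroup analyses, the enrolment summary and the baseline table. That is correct; the gap is only that no overall efficacy model uses it.

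Fourth, the magnitude rests on assumed R² values and on SDs from a different population. The analysed N will probably be below 565, because SAP 6.1.2.2.3 uses observed on-treatment values. This also stands. A smaller N widens both intervals but barely changes their ratio.

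**Conclusion.** The concern holds. The SAP's CD4+ model drops both stratification factors that the protocol includes, and SAP 6.3 is incorrect for this endpoint. No passage explains the removal or dates it.

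The effect on inference is small: a CI 0 to 2.6% wider than under the protocol model for assumed R² of 0 to 0.05, with coverage of about 95.0 to 95.6%. In the Phase 2 illustration the top of that range is worth about 1 cell/µL on a half-width of about 38. There is no bias and no effect on the primary endpoint, its alpha or its power. It should be corrected because the record of what was pre-specified is wrong and the correction is trivial.

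**What to change.** **Option A: restore the protocol model.** In SAP 6.1.2.2.3 and Appendix 8 item 14i, add the two factors as main effects: `class trtgrp nrti resist; model CD4 = trtgrp nrti resist;`. This uses 1 + 2 = 3 extra degrees of freedom. State which strata are used. The as-randomised IWRS values are the natural choice, because protocol 5.1 and the synopsis model describe the same resistance factor; protocol 8.5.2 is less specific. If the re-classified strata of SAP 3.3 and 4.1.1 are preferred, say so and list that in SAP 6.3.

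**Option B: keep treatment only**, for example because the completed Week 48 analysis used it. Correct SAP 6.3 to name the change, its date and its reason, and state which model was used at Week 48.

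Under either option, label any second estimate as supportive.

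The cost is two class terms in one procedure call and a sentence on the strata source, or one corrected sentence in SAP 6.3. No new data are needed. Both versions of the strata are available, since SAP 4.1.1 already provides that "If there are discrepancies between IWRS and collected data with regard to stratum assignment, a listing of the discrepancies will be provided".
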